#### 4. STUDY DESIGN & PROCEDURES (AIM/PHASE 2 ONLY)

##### **Brief Overview of Aim/Phase 2:**

Using a clustered RCT (randomizing practices), we will allocate half of the practices within each health system to the VAX-MOM intervention and the other half to standard of care. We will measure the impact of the intervention on vaccination rates (primary outcomes) and missed opportunities and process metrics (secondary outcomes) (see Table 4). Finally, if VAX-MOM is successful, we will provide the control practices the intervention during Year 3.

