**Table 3: Training Module Content**

Training Topic:	Training Content Details:
Flu & Pertussis 101	General information regarding prevalence/severity of influenza and pertussis disease
	General information regarding benefits of flu/Tdap vaccination
	Benefits of flu/Tdap vaccination within the pregnant population (e.g., benefits of passive immunity)
Communication	Understanding and applying a “Presumptive Recommendation”
	Brief introduction to Motivational Interviewing (MI) and application with vaccine hesitant pregnant women
	Communication Tips & Tricks: Responses to common concerns/questions about vaccines
Optimizing Office Workflow	Optimal methods and organizational/tracking tools
	

• Pre-visit planning and nurse prompts

	

• EHR prompts (Checklists/Text Fields)

	

• Standing orders

	

• Vaccine rate feedback

	

• Vaccine champion and utilization of PDSA cycles

	

• Optimal vaccine documentation (e.g., vaccines given offsite)

	Putting it all together
	

• “Teamwork”- Ensure entire multidisciplinary team trained in utilization of new methods/tools

	

• “Consistency”- Ensure all tools/methods used consistently

	

• “Adjust as Needed”- Use feedback reports & PDSA cycles to reflect on progress and fine-tune accordingly

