**Table 5. EHR Data Extraction Categories**

Primary	

• Flu vaccines received during flu season (Sept-April)

• Tdap vaccines received during 27-36 weeks of pregnancy

Secondary	

• Vaccine refusal (as documented in EHR)

• Missed opportunities for flu and Tdap

• Flu vaccine in prior season

• Covid vaccination

Patient Demographics	

• Race/ethnicity

• Age

• Insurance

• Language

• Parity

Practice Demographics	

• Site

• Provider type (resident, midwife, MD)

- Measure Procedures

Each health system [REDACTED] will have its own “report builder.” The report builder will be in charge of collecting the electronic health record (EHR) data from their own health system and putting it into a format (report) that can be easily understood and analyzed by study staff.

*Bi-Monthly Feedback Reports:* The report builder for each health system will create vaccine rate feedback reports utilizing extracted EHR data for intervention sites on a bi-monthly basis. These reports will be sent either via secure e-mail directly to the study coordinator in each corresponding state, or uploaded to the secure shared Box folder. The study coordinator will then disseminate the vaccination rates for each site to all corresponding site personnel.

For NY health systems, in the event an automated EHR feedback report cannot be generated in time for any given month, the identified vaccine champions or study personnel will estimate flu and Tdap vaccine rates via manual chart review. All vaccine champions and/or study personnel conducting manual chart review will have completed all appropriate eRecord training prior to accessing patient charts. Of those patients who delivered during the identified month, at least 20% will be reviewed. For each chart reviewed, the vaccine champion or study personnel will document the receipt (or lack thereof) of influenza and Tdap immunization as well as Covid vaccination when possible, and will share results with the study team via secure e-mail.

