*Final EHR Data Analysis:* Additionally, at the conclusion of aim/phase 2 (12-month duration) each health system report builder will create a final EHR report for both the intervention sites as well as the control sites capturing updated baseline information from 2019 and 2020 (now needed due to COVID pause), as well as detailed intervention information from 2021 and 2022 (information indicated in Table 5 that was not captured during monthly reports). These final reports will be uploaded to a shared folder on the secure Box platform, accessible by select study staff [REDACTED].

[REDACTED] This report will allow for the comparison of vaccination rates and secondary outcomes

between intervention and control sites. In the event that the final automated EHR reports cannot be generated in a timely manner by the report builders, study personnel and/or a medical student (after being added to the study protocol) will conduct manual EHR chart reviews to collect the data. They will be appropriately trained in the EHR system requiring access, prior to conducting the chart reviews.

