## **Patient-Level Study Subjects**

### **Criteria for EHR Data from Practice Patients (Pregnant Women):**

Baseline vaccine rates for each practice site were established during aim/phase 1 of the study, and contained EHR information from practice patients who were identified as having a live birth within the time period of summer 2018 to summer 2019. Due to a COVID-19 related pause in study activity, updated baseline vaccine rates will also be obtained during aim/phase 2 for the 2019-2020 time period. All subjects are female and some are <18 years of age.

To establish vaccine rates for the ongoing feedback reports, EHR information will be collected bi-monthly (every 2 months) from intervention sites during the entirety of the intervention phase (see timeline depicted in Figure 2). EHR information will reflect practice patients who are identified as being eligible for flu or Tdap vaccine within the specified 2-month time period. Again, all subjects will be female and may be <18 years of age.

To establish the final vaccine data reports (for intervention vs. control comparison), detailed EHR information (see Table 5) will be collected from both intervention and control sites for the 2021-2022 time period.

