## 17. DATA ANALYSIS PLAN

Primary outcomes (receipt of Flu and Tdap vaccines) are binary and our main explanatory variable will be an indicator for study arm. We will employ intent-to-treat analyses using generalized linear mixed models (GLMMs) with practice random effects, an approach recommended for group-randomized RCTs in which the goal is to estimate the causal effects of interventions on individuals, adjusted for clustering within groups. This method performs well in situations where the number of observations per cluster is large and for unequal cluster sizes. Models will assume a binomial distribution and a log link function in order to compare vaccination rates between study arms in terms of risk ratios. We will adjust for all practice-level variables included in the randomization balancing criterion, as well as patient-level race/ethnicity (and prior year vaccination status for the flu analysis). Hypothesis tests will be two-sided with alpha = 0.025, reflecting a 2-fold Bonferroni correction for the co-primary endpoints of Flu and Tdap vaccination status, ensuring a familywise type I error rate of 0.05. Analyses will be performed using SAS v. 9.4 (SAS Institute Inc., Cary, NC).

Power Analysis: We assume national vaccine rates for flu (49%) and Tdap (54%). Adjusting for clustering of patients in practices, and assuming an intraclass correlation (ICC) of 1% (consistent with previous work), this sample size provides >80% power to detect an overall increase of 6.3 percentage point increase in vaccination rates between the QI intervention and control arms. This assumes a chi-squared test (a simplification of the planned mixed model analysis described above), a test-level alpha of 0.025, and a sample size of 5,000 pregnant women organized into 16 practices per study arm.

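### The primary flu model adjusts for prior-year flu vaccination taken from the end-of-trial EHR extract, a covariate the intervention's documentation training could change, so the adjustment itself could pull the flu risk ratio down

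*Combined protocol and SAP*

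**What the plan says.** Section 17 specifies a log-link binomial mixed model for each co-primary endpoint. It adjusts for the practice-level balancing variables and for "patient-level race/ethnicity (and prior year vaccination status for the flu analysis".

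Section 17 does not say where prior-year status comes from. The only matching item in the documents is the Table 5 extraction field "Flu vaccine in prior season". Under Final EHR Data Analysis in Section 4, "at the conclusion of aim/phase 2 (12-month duration) each health system report builder will create a final EHR report", covering intervention and control sites. Section 6 confirms that the Table 5 data for the arm comparison "will be collected from both intervention and control sites for the 2021-2022 time period".

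Table 3 lists, among the training content, "Optimal vaccine documentation (e.g., vaccines given offsite". Section 4 says the study will "allocate half of the practices within each health system to the VAX-MOM intervention and the other half to standard of care". If the programme succeeds, "we will provide the control practices the intervention during Year 3". Controls are therefore untrained throughout the comparison.

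Table 4 also lists flu vaccine in the prior year as a subgroup for the vaccination rates.

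The text supplied gives no chart-entry cut-off for prior-year status, no rule for uncharted status, and no flu analysis without this covariate.

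**The concern.** Randomisation balances true prior-year vaccination between arms in expectation. It does not balance charted prior-year vaccination if one arm has been taught to chart better before the field is read. The covariate is then a post-randomisation variable that the arm can change.

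Suppose intervention practices chart more prior-season doses. Some women who were truly vaccinated last season, and who tend to accept vaccine again, move out of the uncharted stratum in that arm only. The control uncharted stratum keeps them, so its current-season uptake is higher. Comparing arms within strata of charted status then sets a less accepting intervention group against a more accepting control group. This would happen even if every current-season dose were captured perfectly.

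At stake is a co-primary estimate, altered by a term presumably included for precision. The prior-year subgroup would also sort women into strata differently by arm.

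**Working it through.** **1. The plan's own figure.** Section 17 gives 5,000 women in 16 practices per arm, ICC 1%, two-sided alpha 0.025, flu 49% and a 6.3-point increase.
- Women per practice: 5,000 / 16 = 312.5. Design effect: 1 + (312.5 − 1) × 0.01 = 4.115. Effective n per arm: 5,000 / 4.115 = 1,215.
- SE = √[(0.49 × 0.51 + 0.553 × 0.447) / 1,215] = 0.0202. Power = Φ(0.063 / 0.0202 − 2.241) ≈ 81%.
- This reproduces the stated figure of more than 80%. Reading 5,000 as the total gives about 71%, so 5,000 per arm is the reading that fits. Step 5 uses it.

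**2. Assumptions for the bias.** The documents give no figures for these inputs: 35–45% truly vaccinated last season; current uptake 75–85% in those women; uptake in the others (about 20–35%) set so that the overall rate is the plan's 49%; 60% of prior doses charted in control and 65%, 70% or 80% in intervention; no false charting; no true arm effect.

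**3. One case by hand.** Take 40% truly vaccinated and uptake 80% in those women. Uptake in the others is (0.49 − 0.40 × 0.80) / 0.60 = 0.283, so they contribute 0.60 × 0.283 = 0.17. Among women charted as vaccinated last season, uptake is 0.80 in both arms. Among those not charted:

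| Prior doses charted | Uptake in the uncharted stratum | Ratio to control |
|---|---|---|
| Control, 60% | (0.16 × 0.80 + 0.17) / 0.76 = 0.392 | – |
| Intervention, 65% | (0.14 × 0.80 + 0.17) / 0.74 = 0.381 | 0.972 |
| Intervention, 70% | (0.12 × 0.80 + 0.17) / 0.72 = 0.369 | 0.942 |
| Intervention, 80% | (0.08 × 0.80 + 0.17) / 0.68 = 0.344 | 0.878 |

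Crude uptake is 49% in both arms, so the unadjusted risk ratio is 1. A log-binomial fit of arm plus charted status to these expected frequencies combines the strata and gives adjusted risk ratios of 0.991, 0.982 and 0.965.

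**4. Range.** The same fit over all combinations of 35, 40 and 45% truly vaccinated with 75, 80 and 85% uptake:
- equal charting: 1.000
- 5-point gap: 0.990–0.992
- 10-point gap: 0.980–0.985
- 20-point gap: 0.960–0.971

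With a true effect at the plan's size (0.553 / 0.49 = 1.129), 49% truly vaccinated, prior vaccinees two to three times as likely to be vaccinated, and 70% against 80% charted, the adjusted risk ratio is 1.107–1.108. On a 49% base that is about 5.3 points instead of 6.3.

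**5. Precision at stake if the covariate is dropped.** The within-practice share of the variance of an arm's rate is (1 − 0.01) / 4.115 = 24%. A patient-level covariate acts mainly on that share. Differences between practices are partly covered by the baseline flu rate, which stays in the model.

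**6. The opposing bias.** If the same training raised capture of current-season doses from an assumed 90% to 95%, the risk ratio would be multiplied by 0.95 / 0.90 = 1.056. Combined with the 60% against 80% covariate gap and no true effect, the net risk ratio is about 1.01–1.02, above 1.

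**The case against.** The strongest reply is that the premise is inferred. One Table 3 sub-item mentions documentation, within a programme about current flu and Tdap vaccination. Nothing says staff are taught to chart last season's flu dose. This stands: the documents show that the covariate is open to the arm, not that it will be changed.

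Two related points also stand. The date a report is built is not the date a dose was entered, and doses charted before training are unaffected. Section 4 also points to a separate EHR data extraction document, not supplied here, which might define look-back and entry dates.

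On size, gaps of 10 or 20 points have no support in the documents, and a 2-point gap would give a risk ratio of about 0.997. A reader might also convert the bias into a specific loss of power. The documents do not support that: the plan's power rests on an unadjusted chi-squared test, which Section 17 itself calls a simplification. Pairing its SE with a bias from the adjusted model would not describe the planned analysis.

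Finally, better charting of the outcome would push the estimate up and could outweigh this bias. That is correct, but it is a separate problem. Two uncontrolled biases of unknown size cannot be relied on to cancel, and this one arises only because the model includes the term.

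**Conclusion.** The concern holds as a conditional one. The primary flu model conditions on a variable whose only stated source is read after one arm alone was trained in vaccine documentation, and the text supplied contains no safeguard. If that training raises charting of prior-season doses, the adjusted flu risk ratio falls: to about 0.99, 0.98 and 0.96–0.97 for gaps of 5, 10 and 20 points when the truth is 1. These sizes rest on assumed charting rates, prior-year prevalence and strength of association. With equal charting there is no bias.

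A reader might infer that the trial's flu result will be biased toward no effect. The documents do not support that, because the same training may inflate the recorded outcome, so the net direction is unknown. The practice-level baseline rates from Aim 1 precede the training and are not affected. The Tdap model does not include this covariate. The prior-year subgroup is exposed in the same way as the flu model.

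**What to change.** In Section 17, make the flu model without patient-level prior-year status primary. Keep the pre-randomisation practice-level baseline rates, the other balancing variables and race/ethnicity. Report the model adjusted for prior-year status as a sensitivity analysis.

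If the covariate is kept in the primary model, count only prior-season doses whose EHR entry predates the woman's first prenatal visit at the practice, by the same rule in both arms. Use that variable for the Table 4 subgroup as well. A single cut-off at randomisation is less suitable: the documents give no common randomisation date, and women entering care later may have no entry by then.

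The preferred change costs a sentence or two in the SAP and a small loss of precision, since only about 24% of the variance of an arm's rate is within practices under the plan's ICC. It leaves the target unchanged if the risk ratio is the same in both prior-status groups, because risk ratios are then collapsible over a balanced covariate. Keeping the covariate instead costs two extracted dates (dose entry and first prenatal visit) and gives a cruder variable. Neither change addresses differential charting of the outcome, which needs its own safeguard.

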### STUDY SITES & PROJECT STAFF OVERVIEW

[REDACTED], study PI, will ensure study and regulatory compliance, by:

- Participating in routine prescheduled meetings with all project investigators and project staff for the duration of the study, including:
  - *Weekly Core Leadership Team Meetings* (State-level Investigators, study coordinators, all study consultants, data specialist): discussion of global project goals, timeline, regulatory requirements and adherence, protocol requirements and adherence, measure development, e-learning content, data analysis, workflow details, etc.

- *Weekly State-level Team Meetings* (State-level Investigators, study coordinators, data specialist as needed): discussion of day-to-day operations needed to support global study goals (including protocol and regulatory items).
- *Weekly Site-level Team Meetings* (State-level Investigators, study coordinators, Site Investigators, OB/GYN site liaisons, site EHR report builders): discussion of provider/nurse workflow, development of study measures specific to providers/nurses, optimal measure dissemination procedures, identification of possible vaccine champions.
- *Data Development & Analysis Meetings* (State-level Investigators, study coordinators, EHR report builders, data specialists): discussion of data collection methods, EHR data extraction methods, data analysis, data storage/management.
- Keeping all study personnel abreast of *prearranged study changes* and subsequent regulatory determinations (e.g., changes to study measures, workflow procedures, study personnel, etc.) via a predetermined communication chain:
  - Core Leadership Team discusses necessary study change → NY study coordinator submits amendment to RSRB → RSRB notifies Study PI and NY study coordinator of regulatory determination → Study PI and NY coordinator notify Core Leadership Team → As appropriate, both study coordinators will further notify site-level personnel and/or data specialists
  - Communication with study site personnel will most often take place during prescheduled meeting times, but in more urgent cases, will take place as soon as needed.
  - Communication will be both verbal (during or outside of weekly meetings depending upon level of urgency) and written as needed (via e-mail, e-mail attachments, or the secure shared Box folder).

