**Table 6: Participating Practice Sites and Demographic Information (Total Subject Pool)**

NEW YORK PRACTICES:		
Participating Practice	Total Number of Providers	Annual Deliveries
[REDACTED]	35	800
[REDACTED]	9	100
[REDACTED]	12	200
[REDACTED]	18	300
[REDACTED]	16	500
[REDACTED]	2	200
Insurance (% Private/Public/Other)	45/55/5	
Race/Ethnicity (% White/ Black/Hispanic)	65/25/10	
CALIFORNIA PRACTICES:		
Participating Practice	Total Number of Providers	Annual Deliveries
[REDACTED]	10	511
[REDACTED]	4	130
[REDACTED]	6	144
[REDACTED]	3	13
[REDACTED]	7	415
[REDACTED]	4	110
[REDACTED]	4	17
[REDACTED]	3	0
[REDACTED]	5	256
[REDACTED]	1	16
[REDACTED]	5	392
[REDACTED]	6	353
[REDACTED]	3	309
[REDACTED]	3	298
[REDACTED]	6	143
[REDACTED]	3	128
Insurance (% Private/Public/Other)	55/45/5	
Race/Ethnicity (% White/ Black/Hispanic)	65/15/20	

CALIFORNIA PRACTICES:		
Participating Practice	Total Number of Providers	Annual Deliveries
[REDACTED]	13	1792
[REDACTED]	8	300
[REDACTED]	8	1500
[REDACTED]	5	157
[REDACTED]	1	80
[REDACTED]	4	472
[REDACTED]	2	180
Insurance (% Private/Public/Other)	89/1/10	
Race/Ethnicity (% White/ Black/Hispanic)	52/7/13 & 14% Asian	
[REDACTED]		
Participating Practice	Total Number of Providers	Annual Deliveries
[REDACTED]	5	≈800
[REDACTED]	7	≈1000
[REDACTED]	3	≈450
[REDACTED]	3	≈450
[REDACTED]	2	≈250
[REDACTED]	1	≈150
[REDACTED]	9	≈1000
[REDACTED]	3	≈500
Insurance (% Private/Public/Other)	20/75/5	
Race/Ethnicity (% White/ Black/Hispanic)	15/25/55 & 5% Asian	

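### Optional improvement, not an error: the fixed Bonferroni split for flu and Tdap is valid, but Holm's step-down test keeps familywise error at 0.05 and gives the second vaccine more power

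*Combined protocol and SAP*

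**What the plan says.** Section 17 (Data Analysis Plan) names two primary outcomes: "Primary outcomes (receipt of Flu and Tdap vaccines) are binary". It gives the decision rule as "Hypothesis tests will be two-sided with alpha = 0.025, reflecting a 2-fold Bonferroni correction for the co-primary endpoints of Flu and Tdap vaccination status", with the stated purpose of "ensuring a familywise type I error rate of 0.05". The Power Analysis paragraph uses the same test-level 0.025 and qualifies its figure: "This assumes a chi-squared test (a simplification of the planned mixed model analysis described above". Neither document section adds a step-down rule, a testing order or any passing of alpha from one endpoint to the other.

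Two other places bear on the point. Section 4, Step 3 speaks of a single primary outcome that covers both vaccination rates, whereas section 17 calls them co-primary. Section 4 (Final EHR Data Analysis) has each report builder, at the end of the 12 months, "create a final EHR report for both the intervention sites as well as the control sites"; this is the first scheduled report covering both arms.

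**The concern.** Nothing in the rule is wrong. The question is whether it gives away power for no gain in error control. After one vaccine has been declared significant at 0.025, at most one true null hypothesis can remain, so the remaining test may use the full 0.05. Under the fixed rule, a second vaccine with p = 0.03 after a clear result on the first is declared not significant, although the familywise 0.05 that the plan sets for itself would allow the rejection.

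At stake is the chance of a correct positive finding on the second vaccine, with no more practices or women. The estimates, the costs and the cost-effectiveness ratios are untouched.

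**Working it through.** **1. The plan's own figures.** Inputs from section 17: control rates 49% (flu) and 54% (Tdap), an increase of 6.3 points, ICC 0.01, alpha 0.025 two-sided, and 5,000 women in 16 practices, read as per arm.

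- Familywise alpha: 0.025 + 0.025 = 0.05, as stated.
- Mean practice size: 5,000/16 = 312.5. Design effect: 1 + (312.5 − 1) × 0.01 = 4.115. Effective size: 5,000/4.115 = 1,215 per arm.
- Flu: SE = √[(0.49×0.51 + 0.553×0.447)/1,215] = 0.02023; 0.063/0.02023 = 3.115; power = Φ(3.115 − 2.2414) = 80.9%.
- Tdap: SE = 0.02004; 0.063/0.02004 = 3.144; power = 81.7%.
- Using the pooled variance for the critical value gives 80.75% and 81.55%. Either way the stated >80% is reproduced. With 5,000 women in total, power would be 70.9% and 71.8%, so the per-arm reading is the one that fits.

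**2. Why Holm keeps the 0.05.** If both nulls are true, Holm makes a false rejection only if the smaller p-value is at or below 0.025, exactly as Bonferroni does; the bound is 2 × 0.025. If one null is true, Holm never tests it above 0.05. Neither argument uses the correlation. With both nulls true, familywise error is 4.9, 4.7 and 3.6% at correlations 0, 0.5 and 0.9 under either rule.

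**3. Power gain, base case.** Let c₁ = 2.2414 (0.025), c₂ = 1.9600 (0.05), and B = P(|Z₁|>c₁, |Z₂|>c₁). With 80% power each, the non-centrality is 2.2414 + 0.8416 = 3.0830.

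- Holm, both: P(|Z₁|>c₁, |Z₂|>c₂) + P(|Z₁|>c₂, |Z₂|>c₁) − B
- Holm, endpoint 1: P(|Z₁|>c₁) + P(|Z₁|>c₂, |Z₂|>c₁) − B
- At least one, either rule: 0.80 + 0.80 − B

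At correlation 0, P(|Z|>c₂) = Φ(3.0830 − 1.9600) = 0.8693. Both: 2 × 0.8693 × 0.80 − 0.64 = 0.751. Per endpoint: 0.80 + 0.8693 × 0.80 − 0.64 = 0.855. The other columns use exact bivariate normal probabilities.

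| Correlation (assumed) | 0 | 0.5 | 0.9 |
|---|---|---|---|
| Per endpoint, Bonferroni | 80.0% | 80.0% | 80.0% |
| Per endpoint, Holm | 85.5% | 84.6% | 83.2% |
| Both, Bonferroni | 64.0% | 68.7% | 75.0% |
| Both, Holm | 75.1% | 77.8% | 81.5% |
| At least one, either rule | 96.0% | 91.3% | 85.0% |

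Zero is the most favourable of the three values and the least plausible for two vaccines given in the same practices. With the plan's own inputs from step 1, power for both goes from 66.1 to 76.8%, 70.5 to 79.3% and 76.5 to 82.7%.

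**4. Unequal effects.** If one vaccine has half the effect (non-centrality 1.5415), its power goes from 24.2% to 31.9, 32.9 and 33.8%. If one vaccine has no effect, the false-positive rate on it goes from 2.5% to 4.5, 4.2 and 3.8%. At correlation 0 this is 0.025 + 0.80 × (0.05 − 0.025) = 0.045.

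**5. Unequal practice sizes.** Table 6 lists 37 practices with 0 to 1,792 annual deliveries: total 14,416, mean 389.6, SD 393.2, CV 1.01. Assume that deliveries stand in for analysed women and rescale the sizes to mean 312.5. Mixed-model weighting gives a design effect of Σn / Σ[n/(1 + (n − 1) × 0.01)] = 4.97. Power at 0.025 is then 72.4% (flu) and 73.3% (Tdap), and power for both goes from 53.0 to 65.4%, 59.2 to 69.5% and 66.9 to 74.4%. The levels fall, but the gain does not: 12.3, 10.3 and 7.5 points, against 11.1, 9.1 and 6.5 in the base case.

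**The case against.** The strongest objection is about intervals. Holm's only additional rejections have a p-value between 0.025 and 0.05. If test and interval come from the same model, the 97.5% interval for that risk ratio will include 1 every time. Under the present rule, test and 97.5% interval always agree; Holm gives that up in exactly the cases where it helps. This stands, and it is a sound reason to keep Bonferroni if easy reporting is preferred.

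Second, the plan gives power per test and sets no goal of winning on both vaccines, so the per-endpoint gain of 3.2 to 5.5 points is the fairer headline. That is reasonable, and both measures are given here. The gain also shrinks as the correlation nears 1: in the base case the gain for both is 5.5 points at 0.95 and 3.1 at 0.99.

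Third, the success rule is not spelled out. If both vaccines had to succeed, no alpha split would be needed and Holm would be irrelevant. But splitting alpha makes sense only if either vaccine can succeed alone, and that is the setting in which Holm applies.

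Fourth, a change of decision rule during the trial must be defended. Section 6 describes allocation in the past tense, and study staff see intervention-arm rates every two months. Those rates are single-arm, so they are not a comparison, but the amendment should say what had been seen when it was made.

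**Conclusion.** The point holds as an optional, inexpensive improvement. The present rule controls error as claimed, and its power figure reproduces. Holm gives the same familywise 0.05 under any correlation and loses no rejection. For correlations from 0 to 0.9 with equal effects, it adds about 3 to 5.5 points of power per vaccine in the 80% base case, and about 6 to 12 points for showing both across that case and the Table 6 size variation. It adds nothing to the chance of showing at least one.

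That Holm controls error and keeps every Bonferroni rejection needs no assumption. The size of the gain rests on the assumed correlation, on both vaccines responding, and on a normal approximation in place of the planned mixed model.

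**What to change.** Replace the sentence on hypothesis tests in section 17 with:

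> The two primary endpoints are tested by the Holm procedure at a familywise two-sided 0.05: the smaller p-value against 0.025 and, if significant, the larger against 0.05. Report 97.5% confidence intervals for both risk ratios; the Holm test is the decision rule.

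The power statement at 0.025 can stay; under Holm it is a lower bound for each endpoint. It would also help to say that success on either vaccine counts, and to bring section 4, Step 3 into line with that.

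The cost is two sentences and one amendment by the route in section 3, where the "NY study coordinator submits amendment to RSRB". It must be made before any comparative outcome data are seen. The documents do not show whether the first two-arm report has already been produced; if it has, the fixed split should stay. The sponsor also accepts two consequences: an interval that includes 1 beside each added rejection, and a false-positive rate of about 3.8 to 4.5% instead of 2.5% on one vaccine if only the other responds, which is still within 0.05.
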